### Amendment rationale

The main purpose of the amendment is to clarify that patients who are benefiting from treatment with Afinitor at the time of overall survival analysis may discontinue this study and transition to commercial Afinitor or to a rollover study. The study closure will occur once the last patient last visit (LPLV) in the study has been documented.

A rollover study allows patients to continue to be treated from multiple protocols in one program spanning multiple indications. Patients will be evaluated as per institution's standards and safety will continue to be monitored as per rollover protocol requirements.

Several Novartis rollover studies are available such as the global rollover study: CRAD001C2X01B or local studies (e.g. CRAD001C1X01B in Japan, CRAD001C2XB in Thailand). Choice of rollover studies will be depending on the country/site location. These studies have reduced scheduled assessments for the patients, reduced data collection, queries and monitoring frequencies.

Patients may also transition to commercially available treatments, where possible as per local regulations. Patients will be evaluated as per institution's standards and safety will continue to be monitored as per prescribing information.

In addition, the amendment clarifies the timing of the analysis of progression free survival for second line treatment. This analysis will be performed 18 months after last patient first visit (LPFV) only if there is adequate number of patients in second line treatment at that time. Otherwise, the analysis will be performed 24 months after LPFV at the same time as the overall survival analysis.

To date, enrollment in the study is closed. Last patient first visit was achieved on 17th of December 2014. A total of two hundred and two patients were enrolled in the study. At the release date of this amendment, 127 patients were ongoing in the 1st line treatment setting and 11 patients were ongoing in the 2nd line treatment setting. A total of 20 patients were randomized in the stomatitis therapeutic intervention sub-study.

As mentioned in protocol Section 10.5.4, the overall survival analysis will be performed 24 months after LPFV which occurred on 17th of December 2014.

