### **2.2.1 Stomatitis therapeutic intervention**

Stomatitis, the inflammation of mucous membranes lining the mouth and throat, has been observed in approximately 44-64% of everolimus-treated patients (Afinitor PI). It is also a common adverse event associated with radiation and chemotherapy. Specific strategies to prevent and/or ameliorate the severity of everolimus-associated mucositis are not well documented. Caphosol is an oral mouth rinse indicated as an adjunct to standard oral care in the prevention and treatment of stomatitis caused by radiation or high dose chemotherapy. Low level laser therapy (LLLT) has also been suggested by the Multinational Association of Supportive Care in Cancer (MASCC) and the International Society for Oral Oncology (ISOO) to reduce the incidence of oral stomatitis and its associated pain in patients receiving high dose chemotherapy or chemo-radiotherapy ([Keefe et al 2007](#)). However, mTOR inhibitor-induced stomatitis is a different clinical entity, manifesting more frequently as discrete aphthous-like lesions rather than diffuse inflammation. A recent study evaluated the clinical presentation and management of stomatitis in 17 patients treated with an mTOR inhibitor. The majority of patients were treated with topical corticosteroids including an oral dexamethasone solution which was rinsed and expectorated. Clinical improvement was noted in over 85% of topical corticosteroid-treated patients ([de Oliveira et al 2011](#)). Additional reports from investigators indicate that an oral steroid rinse may help to ameliorate mTOR-induced stomatitis ([name], personal communication, February, 2012 and [name], personal communication, March 2012).

As a secondary endpoint, this trial will assess the effectiveness of treating stomatitis using an alcohol-free 0.5mg/5ml dexamethasone mouth rinse in countries where the solution is commercially available. At the onset of symptoms, enrolled patients will contact their physician. Based on preliminary confirmation of diagnosis, patients will be asked to visit the study site within 24 hours. Upon confirmation of the diagnosis of stomatitis the patient will be

randomly assigned to use either 0.5mg/5ml dexamethasone mouth rinse swished and expectorated 3 times per day or the standard of care normally used to treat stomatitis at the patient's center.

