**Table 3-1 Objectives and related endpoints**

Objective	Endpoint	Analysis
Primary: The primary objective is to estimate progression-free survival in patients treated with everolimus + letrozole in the first line setting.	PFS	Refer to Section 10.4 .
Secondary: Determine the overall response rate and clinical benefit rate of everolimus + letrozole in the first line setting	ORR, CBR	Refer to Section 10.5.1 .
Determine the progression free survival, overall response rate and clinical benefit rate of everolimus + exemestane in second line population	PFS, ORR, CBR	Refer to Section 10.5.2 and Section 10.5.3 .
Evaluate the safety of everolimus + letrozole in the first line setting	Incidence of Adverse events	Refer to Section 10.5.5.2 .
Evaluate the safety of everolimus + exemestane in the second line setting	Incidence of Adverse events	Refer to Section 10.5.5.2 .
Estimate the overall survival of patients treated with everolimus + letrozole in the first line setting	OS	Refer to Section 10.5.4 .
Evaluate a therapeutic intervention to reduce the severity and duration of stomatitis	Oral Stomatitis Daily Questionnaire (OSDQ) data	Refer to Section 10.5.5.1 .
Evaluate clinical benefit as assessed by the Investigator during the Extension Phase	Proportion of patients with clinical benefit as assessed by the Investigator at scheduled visits	Refer to Section 10.5.5.3 .
Evaluate long term safety data	Frequency and severity of AEs/SAEs	Refer to Section 10.5.5.2 .

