### 6.3.2 Treatment assignment for oral stomatitis therapy

Upon diagnosis of stomatitis, patients in countries where the alcohol-free 0.5mg/5ml dexamethasone oral solution is commercially available, will be randomized in 1:1 ratio to take either 0.5mg/5ml dexamethasone mouth rinse or standard of care at the patient's center. The assignment of a patient to a particular cohort will be coordinated by the sponsor. A randomization list will be produced by or under the responsibility of Novartis Drug Supply Management and the Biostatistician. The randomization list will be reviewed by a Biostatistics Quality Assurance Group and locked by them after approval.

During the Extension Phase, standard of care at the patient's site as recommended by the investigator to treat stomatitis will be followed.

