## Other assessments

### 7.2.6 Patient reported outcomes

Patient reported outcome (PRO) and impact of oral stomatitis burden on patient's daily living will be evaluated using the Oral Stomatitis Daily Questionnaire (OSDQ). The PRO will be not be administered during the Extension Phase. Completion of the PRO questionnaire will be dependent on the availability of OSDQ in the local language. The OSDQ is a patient self-administered 6-item questionnaire with a 24-hour recall period. Sample of the questionnaires can be found in the [Appendix 1](#).

The OSDQ is an oral stomatitis-specific exploratory questionnaire developed for the purpose of this study. It is based on prior work by [Stiff et al \(2006\)](#) who developed and validated the Oral Mucositis Daily Questionnaire (OMDQ) to assess impact of oral mucositis on pain and daily functioning in patients undergoing autologous hematopoietic stem cell transplantation (HSCT). Although the OMDQ is available in the public domain (personal communication with the author, March 2012), it does not readily meet the need of this study as it contains diarrhea items more sensitive in measuring the symptoms intrinsic to the HSCT setting.

At the first episode of stomatitis, an OSDQ booklet will be handed out to patients at the study site upon confirmation of an oral stomatitis diagnosis. The booklet will contain 28 copies of the OSDQ, marked from Day 1 to Day 28, to be filled out by the patient up to 28 consecutive days, as long as the episode continues. During first episode of oral stomatitis, Day 1 OSDQ should be filled out on site by the patient. The patient should be given sufficient space and

time to complete the questionnaire. The site personnel should check the OSDQ for completeness and ask the patient to complete any missing responses but should not guide them in any way in their responses. Patient's refusal to complete all or any part of the Day 1 OSDQ should be documented in the study data capture system and should not be captured as a protocol deviation.

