#### **10.5.5 Other secondary objective**

##### **10.5.5.1 Therapeutic intervention for stomatitis**

The secondary objective, to evaluate a therapeutic intervention to reduce the severity and duration of stomatitis, will be performed using the PRO questionnaire OSDQ data from patients in FAS who had an incidence of stomatitis while on study and were enrolled in countries where the alcohol-free 0.5mg/5ml dexamethasone oral solution is commercially available. The analysis for this objective will be based on PRO data for the first incidence of

stomatitis AE. The mean, standard deviation and 95% confidence interval of each severity items in the questionnaire will be calculated at each day for the two therapeutic interventions for stomatitis groups and presented graphically. The duration of the first stomatitis incidence will be calculated using the dates reported in the PRO, the median duration with 95% confidence interval of the first stomatitis AE will be estimated using Kaplan-Meier method for the two therapeutic interventions for stomatitis groups. As supportive analysis, the median duration will also be estimated using the duration calculated from start dates and end dates reported in AE CRFs.

As an exploratory analysis, sensitivity analysis for duration and severity may be performed on PRO data from multiple occurrences on the same patient. In this analysis appropriate methods will be used to account for within patient correlation.

The PRO will be not be administered during the Extension Phase.

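### The randomized stomatitis rinse comparison has no prespecified between-arm effect estimate with a confidence interval, and the Day 1 score is not used as a baseline

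*Protocol*

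**What the plan says.** - **Objective.** Protocol Table 3-1 lists as a secondary objective: "Evaluate a therapeutic intervention to reduce the severity and duration of stomatitis". Section 2.2.1 says that "this trial will assess the effectiveness of treating stomatitis" with the rinse.
- **Allocation.** Under section 6.3.2, patients with diagnosed stomatitis, in countries where the solution is sold, "will be randomized in 1:1 ratio to take either 0.5mg/5ml dexamethasone mouth rinse or standard of care". Section 6.3.3 makes the trial open-label.
- **Severity analysis.** Section 10.5.5.1 uses the first episode. The mean, SD and 95% CI of each severity item "will be calculated at each day for the two therapeutic interventions for stomatitis groups and presented graphically".
- **Duration analysis.** The same section says that median duration, with its 95% CI, "will be estimated using Kaplan-Meier method for the two therapeutic interventions for stomatitis groups". This is repeated from adverse event dates as support. An optional multi-episode analysis accounts for within-patient correlation but names no contrast between arms.
- **Questionnaire.** Section 7.2.6 hands out the OSDQ booklet at the site once the diagnosis is confirmed, and in the first episode "Day 1 OSDQ should be filled out on site by the patient". Recall is 24 hours. The form is then completed daily for at most 28 days, and only while the episode lasts.
- **Size.** Section 10.8 bases the sample size on the precision of first-line median PFS and gives nothing for this sub-study. The Amendment 4 rationale reports: "A total of 20 patients were randomized in the stomatitis therapeutic intervention sub-study".

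**The concern.** To reduce severity and duration is a claim relative to the other arm, and randomization was introduced to support it. The analysis nevertheless stops at a description of each arm. A report that follows section 10.5.5.1 exactly would contain two sets of daily means and two medians, but no statement of how much the rinse changed either outcome or how uncertain that change is. The choice of day, item and contrast would be made after the data are seen.

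Two features add to this. A Day 1 score is collected at diagnosis and is likely to be prognostic, but neither a change from Day 1 nor an adjustment for it is planned. And since patients stop completing the form when they recover, the curves at later days can describe a shrinking, selected group. If the rinse shortens episodes, those still reporting in the rinse arm are the slower resolvers, and the plotted means could look no better than control even though the rinse works.

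**Working it through.** The protocol states no size, power or precision for the sub-study, so there is no figure of its own to reproduce. The check has two parts: what the specified outputs can deliver, and what a prespecified contrast would deliver.

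**1. What the specified outputs deliver**

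- Table 14-1 has nine scored responses (Q2, Q3, Q4a to Q4e, Q5, Q6). Over up to 28 days that is up to 9 × 28 = 252 pairs of means if every scored item counts as a severity item, with no item or day singled out.
- An unadjusted daily difference, and a CI for it, can be derived from each arm's mean, SD and number of forms. At later days it compares only patients still completing the form.
- A Day 1-adjusted difference cannot be derived, because it needs the within-patient correlation between Day 1 and later scores, which separate daily summaries do not show.
- The difference in median duration follows by subtraction. A hazard ratio or restricted-mean difference does not follow from two medians.

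**2. What a contrast would deliver**

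Inputs: 20 randomized (Amendment 4 rationale) at 1:1 (section 6.3.2). The arm split is not given; 10 and 10 is assumed. The correlation r between the Day 1 and later scores is not given; 0.3 to 0.7 is assumed.

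*Severity.* Half-width of the 95% CI for the difference in means, in SD units = t × √[(2/10)(1 − r²)], with 18 degrees of freedom unadjusted and 17 with one covariate.

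| r | Variance factor 1 − r² | Half-width |
|---|---|---|
| unadjusted | 1 | 2.101 × 0.447 = 0.94 SD |
| 0.3 | 0.91 | 2.110 × 0.427 = 0.90 SD |
| 0.5 | 0.75 | 2.110 × 0.387 = 0.82 SD |
| 0.7 | 0.51 | 2.110 × 0.319 = 0.67 SD |

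*Duration.* With d resolution events split evenly, SE(log HR) = √(4/d), and the 95% CI is the estimate divided and multiplied by exp(1.96 × √(4/d)).

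- d = 20: exp(1.96 × 0.447) = 2.40
- d = 16: exp(1.96 × 0.5) = 2.66

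*Power, for orientation only* (normal approximation, two-sided 5%, unadjusted):

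- 0.5 SD: Φ(0.5/0.447 − 1.96) = Φ(−0.84), about 20%
- 0.8 SD: Φ(0.8/0.447 − 1.96) = Φ(−0.17), about 43%
- HR 0.5 with 20 events: Φ(0.693/0.447 − 1.96) = Φ(−0.41), about 34%

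Adjustment gives a materially tighter estimate if the Day 1 score is as correlated as assumed. It does not make the sub-study a powered test.

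**The case against.** The strongest reply is that the form of a contrast, its covariates and its window belong in the SAP, which is not at hand, and that section 10.5.5.1 does not forbid one. The trial is estimation-based throughout: PFS and OS are also reported as Kaplan-Meier medians with CIs and no hypothesis. The OSDQ is described as exploratory, the sub-study is small and open-label, and the objective asks only for an evaluation.

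Part of this stands. The model can be left to the SAP, and a descriptive style is reasonable for the single-arm endpoints, which have no comparator. But for the randomized part the protocol does not leave the method open. It names the population, episode, statistics and display, and all of them are within-arm. An SAP that follows it as written yields no treatment effect.

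Three further objections stand as limits:

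- The count of 20 is a snapshot, taken with 127 first-line and 11 second-line patients still on treatment, and is not a design figure.
- Section 7.2.6 does not say whether the Day 1 form precedes assignment or the first rinse. That it reflects the state before treatment is inferred from on-site completion and 24-hour recall. Patients may also refuse it in whole or in part.
- A mean over a fixed window has scores absent by design after recovery, so the contrast needs an explicit rule for those days.

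A reader might also infer that chance imbalance on Day 1 could be as large as a sizeable treatment effect. That is not supported: with 10 per arm the SE of the Day 1 difference is √(2/10) = 0.447 SD, so an imbalance of 1 SD or more has a probability of about 2.5% (z = 2.24). The reason to adjust is precision and a cleaner comparison.

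**Conclusion.** The concern holds in a limited form. For the trial's only randomized comparison, the protocol fixes a per-arm descriptive analysis. It prespecifies no between-arm estimate with a CI, does not use the Day 1 score as a baseline, and plots daily means that may progressively exclude recovered patients. This affects one secondary objective and leaves the primary endpoint untouched. It should be corrected because correction is cheap, but it does not threaten the trial.

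Two stronger readings go too far. A reader might infer that the objective cannot be answered at all; in fact both arms are shown side by side, the Day 1 values are displayed, and an unadjusted difference can be worked out from the output. A reader might also infer that the arms are to be judged by whether their confidence intervals overlap; the protocol states no such rule, so error rates for it say nothing about this plan.

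The gain rests on the assumed 10 per arm and Day 1 correlation: a half-width of 0.94 SD unadjusted, 0.82 SD at r = 0.5 and 0.67 SD at r = 0.7. Even after the change the result is an imprecise estimate.

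**What to change.** Add to section 10.5.5.1, for the first episode and by randomized arm:

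1. **Severity:** the between-arm difference in mean mouth-pain score (Q5) and mean soreness score (Q3) over a fixed window after Day 1, adjusted for the Day 1 score of the same item, with a 95% CI. State the window, the rule for days after recovery (for example, scored 0, the no-pain and no-soreness value on these items), and the handling of missing Day 1 forms.
2. **Duration:** a between-arm hazard ratio or restricted-mean difference for time to resolution, with a 95% CI, alongside the two Kaplan-Meier medians.
3. **Labelling:** keep the daily plots as descriptive, with the number of patients contributing on each day. State that the comparison is for estimation and is not powered.

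The cost is a short change to the protocol or SAP wording and a modest amount of programming. No new data, visits or patients are needed.

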#### **10.5.5.2 Safety**

The assessment of safety will be based mainly on the frequency of adverse events and on the number of laboratory values that fall outside of pre-determined ranges. Other safety data (e.g., electrocardiogram, vital signs) will be considered as appropriate. All safety data collected will be listed. For all safety analyses, the safety population will be used. The safety summary tables will include only assessments collected no later than 28 days after study drug discontinuation.

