### Changes to the protocol

The changes to the protocol are as follows:

- Locally advanced, HER2 negative breast cancer patients:
  - The title has been updated to include locally advanced, HER2 negative breast cancer patients as defined in inclusion criteria #1
  - Throughout the entire document, relevant sections have been updated to include HER2 negative, locally advanced breast cancer patients in line with inclusion criteria #1
- Objectives and endpoints:
  - Table 3-1 was updated to include ORR to be in line with secondary endpoints described in Section 10.5.3
- Radiology:
  - Table 7-1 was updated to include CT or MRI for brain as clinically indicated, during the study
  - Section 7.2.1 changed 'Each center must have a designated radiologist who is responsible for the interpretation of CT or MRI' to 'If possible, each center should have a designated radiologist responsible for the interpretation of CT or MRI scans and the evaluation according to RECIST version 1.0 criteria (see Appendix 2 for details)'

- Section 7.2.1: +/- 1 week was added as a window for tumor assessments
- Table 7-3: +/- 1 week was added as a window for CT and MRI procedures and bone scan or skeletal surveys
- Throughout the document references to RECIST have been updated to reflect RECIST version 1.0 used in this trial
- Visit assessment:
  - Visit assessment window of +/- 3 days has been added (except for on-study imaging assessments for which window is +/- 1 week)
- Clinical Benefit Rate:
  - The protocol summary section and Section 10.5.1 have been updated to include the definition of clinical benefit rate
  - CBR defined as the proportion of patients with best overall response of CR, PR or SD with a duration of 24 weeks or longer according to RECIST version 1.0
  - Sections 10.5.1 and 10.5.3 have been corrected to include CBR to be in line with secondary endpoints.
  - Section 10.5.3 has been updated to correct a typo to replace 'median PFS' by 'ORR and CBR'
- Start date for progression Free Survival and Overall survival
  - In Section 10.4.1, starting date for PFS in the first-line setting has been corrected to 'date of enrollment' to be in line with the definition provided in the protocol summary and the definition of the Full Analysis Set
  - Similarly in Section 10.5.4, starting date for OS has been corrected to 'date of enrollment'
- Dexamethasone therapeutic intervention:

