**Table 6-7 Guidelines for management of hepatitis B reactivation**

HBV reactivation (with or without clinical signs and symptoms)*	
For patients with baseline results: Positive HBV-DNA OR positive HBs Ag	Treat: Start a second antiviral AND Interrupt study drug administration until resolution: ≤ baseline HBV-DNA levels If resolution occurs within ≤ 28 days study drug should be re-started at one dose lower, if available. (see Table 6-10 – Study drug dose reductions) If the patient is already receiving the lowest dose of study drug according to the protocol, the patient should restart at the same dose after resolution. Both antiviral therapies should continue at least 4 weeks after last dose of study treatment. If resolution occurs > 28 days Patients should discontinue study drug but continue both antiviral therapies at least 4 weeks after last dose of study treatment.
reactivation is defined as: [Increase of 1 log in HBV-DNA relative to baseline HBV-DNA value OR new appearance of measurable HBV-DNA]	
For patients with baseline results: Negative HBV-DNA and HBsAg AND [Positive HBs Ab (with no prior history of vaccination against HBV), OR positive HBc Ab]	Treat: Start first antiviral medication AND Interrupt study treatment administration until resolution: ≤ undetectable (negative) HBV-DNA levels If resolution occurs within ≤ 28 days study drug should be re-started at one dose lower, if available. (see Table 6-10 – Study drug dose reductions) If the patient is already receiving the lowest dose of either study treatment according to the protocol, the patient should restart at the same dose after resolution. Antiviral therapy should continue at least 4 weeks after last dose of study treatment. If resolution occurs > 28 days Patients should discontinue study drug but continue antiviral therapy at least 4 weeks after last dose of study treatment.
reactivation is defined as: New appearance of measurable HBV-DNA	

\* All reactivations of hepatitis B are to be recorded as grade 3 (CTCAE v 4.0 Metabolic Laboratory/Other: Viral Re-activation), unless considered life threatening by the investigator; in which case they should be recorded as grade 4 (CTCAE v 4.0 Metabolic Laboratory/Other: Viral Re-activation). Date of viral reactivation is the date on which the rise or reappearance of HBV-DNA was recorded.

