**Table 7-2 Visit evaluation schedule (Core Phase: Second-line treatment)**

	Category	Reference to Section	Cycles* 1 cycle = 28 days				End of treatment (EoT) for second line treatment	28 Day Safety Follow up*	Study Evaluation Completion*	Survival follow up**	Post Treatment Evaluations
Cycle Number			Cycle 101	C102	C103	Subsequent cycles					
Visit Number			102	103	104	105, 106, 107...	779	501	778		
Day of cycle			Day 1 of each cycle				Last dose + ≤15 days	Last dose + 28 days			
Inclusion/exclusion criteria re-examination	S/D	7.1.3.	X								
Concomitant medications	D	7.1.1.4.	Continuous during the study up to 28 days after last treatment								
Physical examination	S	7.2.2.1.	Day 1 of each cycle				X				
ECOG Performance status	D	7.2.2.4.	Day 1 of each cycle				X				
Weight	D	7.2.2.3.	Day 1 of each cycle				X				
Vital signs	D	7.2.2.2.	Day 1 of each cycle				X				
ECG	D	7.2.2.6.1.	As clinically indicated								
Pulmonary function test (PFTs)	D	7.2.2.7.	As clinically indicated								
Laboratory assessments:		7.2.2.5.									
Hematology	D	7.2.2.5.1.	Day 1 of each cycle				X				
Chemistry	D	7.2.2.5.2.	Day 1 of each cycle				X				
Coagulation	D	7.2.2.5.3.	As clinically indicated								
Urinalysis	D	7.2.2.5.6.	As clinically indicated								

	Category	Reference to Section	Cycles* 1 cycle = 28 days				End of treatment (EoT) for second line treatment	28 Day Safety Follow up*	Study Evaluation Completion*	Survival follow up**	Post Treatment Evaluations		
Cycle Number			Cycle 101	C102	C103	Subsequent cycles							
Visit Number			102	103	104	105, 106, 107...	779	501	778				
Day of cycle			Day 1 of each cycle				Last dose + ≤15 days	Last dose + 28 days					
Hepatitis testing	D	7.2.2.5.4. 7.2.2.5.5.											
Imaging:		7.2.1.											
CT or MRI for Brain	D	7.1.1.4.	As clinically indicated										
CT or MRI for chest, abdomen, pelvis	D	7.2.1.		X	Every 8 weeks		X only for patients discontinuing for reasons other than documented PD, lost to follow up and death				X		
If bone scan positive perform X-ray, CT or MRI	D	7.2.1.		X	Every 8 weeks		X only for patients discontinuing for reasons other than documented PD, lost to follow up and death						
Safety:		7.2.2.											
Adverse events	D	7.2.2.	Continuous during the study, up to 28 days after the last treatment				X						

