Patient reported Outcomes – OSDQ		7.2.6.	Complete OSDQ daily during every episode of oral stomatitis.										
Everolimus administration	D	6.1.	Daily dosing										
Exemestane administration	D	6.1.	Daily dosing after initial progression for SECOND-LINE TREATMENT ONLY										

	Category	Reference to Section	Cycles* 1 cycle = 28 days				End of treatment (EoT) for second line treatment	28 Day Safety Follow up*	Study Evaluation Completion*	Survival follow up**	Post Treatment Evaluations
Cycle Number			Cycle 101	C102	C103	Subsequent cycles					
Visit Number			102	103	104	105, 106, 107...	779	501	778		
Day of cycle			Day 1 of each cycle				Last dose + ≤15 days	Last dose + 28 days			
Study Evaluation Completion	D	7.1.6.1.						X			
Survival Follow Up	D	7.1.6.2.							X		
Antineoplastic therapies since discontinuation of study treatment	D	5.						X			X

Visit assessment window is defined as +/- 3 days except for on-study imaging assessment: +/- 1 week.

\*Once the patient starts the Extension Phase those indicated will not be performed as part of the main study phase, refer to Table 7-3 for all that will be performed in the Extension Phase.

\*\*Survival Follow-up will only be collected until 24 Months post LPFV (date of OS data cutoff).

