#### 7.2.2.5.4 HBV testing

Prior to enrollment, the categories of patients listed in [Section 7.1.1.3](#) should be tested for hepatitis B serologic markers and viral load (local results are acceptable for screening only):

- HBV-DNA, HBsAg, HBc Ab, and HBs Ab.
- During the treatment period, HBV DNA monitoring should be done depending on results from serologic markers and viral load as listed in [Table 6-6](#).
- The final monitoring visit for HBV will be at the 28-day safety follow-up.

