#### 7.2.2.5.5 HCV testing

Patients with hepatitis C risk factors and at the discretion of the investigator should be tested for HCV RNA prior to enrollment (local results are acceptable for screening only). For a list of hepatitis C risk factors, refer to [Section 7.1.1.3](#).

Follow-up testing will be performed, as per the visit schedule (see [Section 6.2.2.3](#)), only if the patient has a history of Hepatitis C. The final monitoring visit for HCV will be at the 28-day safety follow-up.

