## **8 Safety monitoring and reporting**

### **8.1 Adverse events**

#### **8.1.1 Definitions and reporting**

An adverse event is defined as the appearance of (or worsening of any pre-existing) undesirable sign(s), symptom(s), or medical condition(s) that occur after patient's signed informed consent has been obtained. Please refer to [Section 6.1](#) for the protocol specific definition of study treatment.

Abnormal laboratory values or test results occurring after informed consent constitute adverse events only if they induce clinical signs or symptoms, are considered clinically significant, require therapy (e.g., hematologic abnormality that requires transfusion or hematological stem cell support), or require changes in study medication(s).

Except for screening failures, adverse events that begin or worsen after informed consent should be recorded in the Adverse Events CRF. Conditions that were already present at the time of informed consent should be recorded in the Relevant Medical History/Current Medical Conditions of the patient's CRF. Adverse event monitoring should be continued for at least 28 days following the last dose of study treatment. Adverse events (including lab abnormalities that constitute AEs) should be described using a diagnosis whenever possible, rather than individual underlying signs and symptoms. When a clear diagnosis cannot be identified, each sign or symptom should be reported as a separate Adverse Event. Adverse events will be assessed according to the Common Terminology Criteria for Adverse Events (CTCAE) version 4.0.

If CTCAE grading does not exist for an adverse event, the severity of mild, moderate, severe, and life-threatening, corresponding to Grades 1 - 4, will be used. CTCAE Grade 5 (death) will not be used in this study; rather, information about deaths will be collected through End of Treatment eCRF, Study Evaluation Completion eCRF and/or Survival information.

The occurrence of adverse events should be sought by non-directive questioning of the patient (subject) during the screening process after signing informed consent and at each visit during the study. Adverse events also may be detected when they are volunteered by the patient (subject) during the screening process or between visits, or through physical examination, laboratory test, or other assessments. As far as possible, each adverse event should be evaluated to determine:

1. The severity grade (CTCAE Grade 1-4)

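### The safety tables cut by collection date at day 28, so findings from an on-schedule 28-day follow-up visit held on days 29 to 31 would miss them (minor)

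*Protocol*

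**What the plan says.** Section 10.5.5.2 of the protocol sets the limit for the tables: "The safety summary tables will include only assessments collected no later than 28 days after study drug discontinuation". The same paragraph says that all collected safety data will be listed, without a time limit.

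Table 7-2 (second line, Core Phase) places the 28-day safety follow-up, visit 501, at "Last dose + 28 days". Its footnote reads: "Visit assessment window is defined as +/- 3 days except for on-study imaging assessment: +/- 1 week". Table 7-1 (first line) has the same visit at the same nominal time. Table 7-3 (Extension Phase) also has it, but gives a window only for the 12-weekly visits.

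Sections 7.1.3 and 7.1.4 use this visit to check continuing and new adverse events. The last hepatitis tests are placed there too: "The final monitoring visit for HBV will be at the 28-day safety follow-up" (Section 7.2.2.5.4) and "The final monitoring visit for HCV will be at the 28-day safety follow-up" (Section 7.2.2.5.5). On dating a hepatitis B event, the footnote to Table 6-7 says: "Date of viral reactivation is the date on which the rise or reappearance of HBV-DNA was recorded". Section 8.1.1 sets a minimum for follow-up: "Adverse event monitoring should be continued for at least 28 days following the last dose of study treatment".

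**The concern.** The upper limit of the tables coincides with the nominal day of the visit that supplies the last safety data, and the limit makes no allowance for that visit's window. It is also worded by when an assessment was collected, not by when an event began. An adverse event starting on day 20 is counted if the patient is seen on day 27 and, on the literal wording, not counted if she is seen on day 30. Both visits comply with the schedule.

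The endpoint for the safety objectives in Table 3-1 is the incidence of adverse events, and incidence is read from the tables. Any effect runs one way, towards fewer late events. Hepatitis B reactivation matters most here because Table 6-7 has it recorded as grade 3, or grade 4 if life-threatening.

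**Working it through.** This is date arithmetic. No power, sample-size or alpha figure is involved.

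**Inputs**
- Table cut: day 28 after study drug discontinuation, by collection date (Section 10.5.5.2).
- Nominal day of visit 501: day 28 after the last dose (Tables 7-1, 7-2 and 7-3).
- Visit window: 3 days either side (footnote to Table 7-2).
- End-of-treatment visit: up to 15 days after the last dose (same tables).

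**Discontinuation taken as the last dose**
- Permitted visit days: 28 − 3 = 25 to 28 + 3 = 31, which is 7 days.
- Days past the cut: 29, 30 and 31, which is 3 days.
- Share of permitted days past the cut: 3/7 = 0.429, or 43%.

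If on-schedule visits were spread evenly over the window (an assumption; the protocol gives no distribution), 43% of them would fall past the cut. The possible range is 0% (no visit after day 28) to 100% (all visits on days 29 to 31).

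**Discontinuation taken as the end-of-treatment visit**

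Section 14.2.17 of Appendix 2 dates discontinuation that way for the time-to-event variables. If the visit takes place e days after the last dose, with e from 0 to 15, the cut falls on day 28 + e, that is, day 28 to day 43.

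| e | Cut (day) | Permitted visit days lost |
|---|---|---|
| 0 | 28 | 29, 30, 31 |
| 1 | 29 | 30, 31 |
| 2 | 30 | 31 |
| 3 to 15 | 31 to 43 | none |

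The size of the gap therefore depends on an anchor that Section 10.5.5.2 does not define.

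**What is collected at visit 501**
- Adverse events, and hepatitis B and C monitoring for the patients to whom it applies.
- Hematology, chemistry, vital signs, weight, performance status and physical examination are scheduled at the end-of-treatment visit in Tables 7-1 and 7-2, not at visit 501.

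**Would an onset-date rule alone be enough?**
- An event that began on day 20 and was reported on day 30: yes, onset is by day 28.
- A hepatitis B reactivation first recorded on day 30: no. Table 6-7 dates it to day 30, so a day-28 onset limit still excludes it. The visit window must be covered as well.

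**With the window covered**, the limit for that visit is day 31, and 0 of the 7 permitted days fall outside.

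**The case against.** The best defence is that Section 10.5.5.2 is an ordinary 28-day risk period, loosely worded. Section 8.1.1 records adverse events by start and end date. Section 10.5.5.2.1 says that all recorded events will be summarized and speaks of treatment-emergent events, with no limit on reporting date. The schedules run adverse event collection up to 28 days after the last treatment. On that reading an onset-based window is already meant, and its programming belongs to the analysis plan. This may well be the intention. But the protocol states a rule of its own, and that rule refers to collection. An onset reading also leaves a reactivation first recorded on days 29 to 31 outside.

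Several stronger readings are tempting and are not supported:
- *Follow-up data are discarded.* They are not; everything collected is listed, and only the summary tables are at issue.
- *Late laboratory safety is lost.* Routine laboratory tests are not scheduled at this visit. The shift tables in Section 10.5.5.2.2 cover hematology and biochemistry, and nothing shows that viral-load results would enter a laboratory summary table.
- *Some 43% of late toxicity is missed, or every patient who stops treatment is affected.* The figure counts calendar days under an assumed spread. A patient is affected only if she is seen on days 29 to 31 and also has a newly reported event or a hepatitis sample then.
- *The Extension Phase tables suffer equally.* Table 7-3 states no window for visit 501. The window footnote is legible only under Table 7-2. The Amendment 2 change log describes the window in general terms, but a change log cannot settle the current text.

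**Conclusion.** The point holds as a minor wording fault. For second-line patients the conflict is in the current text: visits on days 29 to 31 are on schedule, and the tables literally exclude what is collected at them. It extends to first-line patients if the same window applies to Table 7-1, which is likely but not visible. For the Extension Phase it cannot be asserted.

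The conclusion assumes that discontinuation means the last dose. The glossary supports this by defining treatment discontinuation as the point when a patient permanently stops taking treatment. With the end-of-treatment visit as anchor, the gap closes once that visit comes 3 or more days after the last dose.

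The data at risk are adverse events first reported on days 29 to 31 and hepatitis results first recorded then. The number is probably small, though the protocol gives nothing from which to calculate it. No efficacy analysis is touched.

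**What to change.** Reword the limit in Section 10.5.5.2 in three parts:
1. Count from the date of last dose and say so.
2. Include adverse events by onset date, no later than 28 days after the last dose, whenever they are reported.
3. Also include assessments made, and adverse events first detected, at the scheduled 28-day safety follow-up visit when it falls within its window, up to day 31.

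Part 3 is needed for a hepatitis reactivation first recorded at that visit. It also admits an event that truly began on days 29 to 31 if it is found there; a table footnote can say so. Stating in Tables 7-1 and 7-3 whether the 3-day window applies to visit 501 would settle the scope.

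The cost is a short rewording and the matching programming rule. No data, visits or clinical procedures change.
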